Cervical cancer screening standard of care:

La Liga mobile units are set up close to busy locations (e.g., a market) in pre-selected communities. Screening is offered 9 am-3:00 pm every weekday for 1-2 weeks per community. Women receive Pap, VIA, breast, thyroid and rectal exams and each clinical encounter typically lasts 15 min (see Table 1). La Liga also has two central administrative offices and clinics (detection centers) where cancer-related screening and treatment is offered by health providers including expert colposcopists, and where administrative staff are based. Training has been conducted on use and reprocessing of the Pocket device, however it is not currently in use in clinics.

Currently, if VIA+ (any evidence of whitening after application of acetic acid; determined at the same time as the exam), women are advised during screening that follow-up clinical evaluation with a medical expert (colposcopist) is required, however no referrals for care are made until Pap smear results are received in about 30 days, unless there is a suspicion of cancer. Patient information and the diagnosis is entered into an electronic database at La Liga (WebLiga). La Liga staff contact women who screen positive and are diagnosed with cervical cancer or pre-cancer to schedule follow-up appointments for care, management and treatment. If the woman misses the colposcopy appointment, La Liga staff call to reschedule. After three attempts at rescheduling, the woman is considered lost-to-follow-up.

Table 1: Standard of care and proposed intervention (mIVAA)

Standard of care	mIVAA
Screen with VIA (IVAA) and Pap in MUs	Screen with VIA, Pap and mIVAA (digital imaging device component) in MUs
No expert review	Expert reviews digital images of the cervix remotely using mIVAA's telemedicine component and refers for follow-up appointments for care, management and treatment, if positive
Refer women for colposcopy based on Pap results 3-4 weeks later	For any women not referred already, refer if needed based on Pap results, per standard of care

Perform diagnostic colposcopy and biopsy and treat, if possible, at central La Liga clinic in Lima	Perform confirmatory colposcopy and biopsy and treat, if possible, at central La Liga clinic in Lima
Additional visits to complete treatment, per standard of care.	Additional visits to complete treatment, per standard of care.

Description of intervention and framework for development:

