This study's intervention will be referred to as mIVAA. mIVAA is comprised of two components: 1) a digital image capture device for magnification and documentation of the cervix during VIA screening done by midwives staffing La Liga's mobile units. Digital imaging devices used in this study will be the Pocket (device developed at Duke University) and/or digital camera of a mobile phone; and 2) a telemedicine platform that enables two-way communication between midwives and colposcopists (Gynecologist-Oncologist). mIVAA can facilitate visual inspection of the cervix through magnification and documentation for midwives, and allows for remote evaluation of cervical images by a colposcopist to determine the need for follow-up clinical evaluation for women with a positive VIA screen.

mIVAA will be implemented in the mobile units (MUs), with support from 1 to 4 expert colposcopists who work at La Liga detection centers in Lima. In the mobile units, midwives will acquire cervical images using a digital imaging device. The images will be transmitted to an expert colposcopists using a mobile device over cellular/WiFi networks.

We will use an adaptation of an existing telemedicine platform developed by MI&T to facilitate the evaluation of cervical images by colposcopists and communication with providers at mobile units. Women being screened in the mobile units will receive an expert evaluation of their cervical images, a management plan and a follow-up appointment for colposcopy and biopsy, as necessary, will be scheduled. As part of the study, we will assess how soon the evaluation, management plan and follow-up appointment are possible after the cervical cancer screening, i.e., within a few hours, same day, within a week etc. For women without suspected lesions, a referral will be possible as per standard of care once Pap results are available and if positive.

Aim 1: To pilot test mIVAA in a community-based setting in Peru.

Methodology:

For this aim, we will enroll approximately 102 women attending any one of five La Liga mobile units for cancer screening, and approximately 18 La Liga health providers and administrative staff.

As part of the pilot, we will:

- Test the feasibility of integrating mIVAA into the existing workflow at the mobile units.
- Assess mIVAA for image quality, network stability, challenges with image transmission, and ability and time to reach experts and receive feedback from experts (two-way communication between health providers).

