Activity 2: Provide feedback on the use of mIVAA through a survey, brief interviews, and/or an individual or group interview. Discussions will assess feedback and satisfaction with the mIVAA system. Individual or group interviews may be completed in person, by phone or by Zoom. The interviews will be audio recorded using an encrypted digital audio recorder, voice recording app on tablet or using Zoom's audio recording function.

Study staff will document in Spanish La Liga provider and staff feedback, and translate to English for analysis and inclusion in any publications. Interviews may be audio recorded, transcribed and translated.

Aim 2: To evaluate effectiveness of mIVAA by comparing the attendance for follow-up clinical evaluation among women screened with mIVAA compared to historical data on women referred for follow-up without mIVAA.

Hypothesis: Use of mIVAA will result in a 13.5% increase in the proportion of screen-positive women completing follow-up clinical evaluation, compared to situations where mIVAA is not used.

Methodology:

For this aim, we will enroll approximately 200 VIA+ women attending any one of five La Liga mobile units for cancer screening, and approximately 18 La Liga health providers and administrative staff. As per standard of care, VIA+ women would be referred for follow-up care. Improving attendance of follow-up care is a primary objective of the study.

As part of the evaluation, we will:

- Assess mIVAA for image quality, network stability, challenges with image transmission, ability and time to reach experts and receive feedback from experts (two-way communication between health providers).
- Assess provider feedback and satisfaction from the use of mIVAA
- Document timing of providing women who screen positive on VIA with colposcopist evaluation of cervical images and management plans based on digital cervical images, and follow-up appointment for confirmatory colposcopy and biopsy.
- Collect survey data from women to identify correlates of follow-up.
- Document rate of follow-up care among women who are referred for management and treatment.
- Abstract historical data from medical records including: clinical notes on Pap results; for women who screened positive on VIA, rates of attending follow-up appointments and colposcopist evaluation; and possible reasons for not attending follow-up appointments.

Study activities with enrolled women

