- Percentage of VIA screened women who are VIA+ (by study arm)
- Average # of days from screening to when a follow-up appointment is scheduled (by study arm)
- Percentage of women who were screened using mIVAA
- Percentage of mIVAA screened women with suspected cancer or pre-cancer by midwife
- Percentage of mIVAA screened women with suspected cancer or pre-cancer by expert
- Average # of days from screening to when expert enters feedback using mIVAA

- Percentage of mIVAA screened women with expert feedback within 0-7 days of mIVAA screening date
- Concordance between midwife and colposcopist on women with suspected cancer or pre-cancer as measured by:
 - Number of women screened positive by midwife
 - Number of women screened positive by expert colposcopist

System outcomes

- Average # of attempts per woman before a readable image is obtained by midwife
- Percentage of mIVAA screened women with at least 1 image rated as readable by expert
- Number of instances of mIVAA failure
- Number of instances of network failure

13. Data & Safety Monitoring:

The risks from participation in the study are considered minimal and commensurate with getting screened with routine methods of cervical cancer screening in Peru such as Pap smears. While no formal data and safety monitoring board is established for this study, study personnel will be instructed to report any unexpected and study-related adverse event to the local study PI in Peru, and Duke PI immediately.

14. Privacy, Data Storage & Confidentiality

Privacy during data collection:

Surveys and interviews will be conducted in mutually agreed upon locations where participants' privacy can be ensured.

Identifying information collected

The study will collect identifying information such as names, dates of birth, and mobile phone numbers to enable the prospective tracking of participants and pulling of medical records. In addition, for women enrolled at the mobile units, data from medical record will be abstracted to measure study outcomes. Mobile phone numbers provided by the participants will be used for any study-related communication.

The study will collect identification information only from health professionals and La Liga personnel, such as participants' names, dates of birth, and mobile phone numbers for reaching out to participants to complete study activities.

Data storage and confidentiality:

Specific actions to maintain confidentiality will include:

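### Mean days to scheduling, by arm, covers only women with a scheduling date, with no rule for the rest and no percentage scheduled beside it

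*Combined protocol and SAP*

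**What the plan says.** Section 12 lists "Average # of days from screening to when a follow-up appointment is scheduled (by study arm" as a secondary process outcome. It does not say who is in the denominator, what happens to a woman with no scheduling date, or over what period dates are sought. No time-to-event method is planned, no test is named for this outcome, and the list contains no percentage scheduled by arm.

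The routes to an appointment are described in Section 5.

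- **Control.** Women are advised at screening, "however no referrals for care are made until Pap smear results are received in about 30 days, unless there is a suspicion of cancer". Table 1 puts it as "Refer women for colposcopy based on Pap results 3-4 weeks later".
- **mIVAA.** After expert review of the images, "a follow-up appointment for colposcopy and biopsy, as necessary, will be scheduled". Table 1 adds a later route: "For any women not referred already, refer if needed based on Pap results, per standard of care".

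The Aim 2 methodology also states: "As per standard of care, VIA+ women would be referred for follow-up care".

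The other timing outcomes in Section 12, such as "Percentage of mIVAA screened women with expert feedback within 0-7 days of mIVAA screening date", apply to mIVAA only.

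**The concern.** Having a scheduling date is an event after screening, and the route to it differs between the arms. In control it depends on the Pap result. Under mIVAA it depends on expert review and then, for those not yet referred, on Pap. The women left without a date may therefore differ between arms in number and in kind. A mean over those who have a date compares two selected groups, and with no percentage scheduled reported a reader could not see the selection.

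Section 10 names possibly earlier referral as the benefit to women, and this is the only timing outcome compared by arm. What is at stake is the size of the reported gain in speed.

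**Working it through.** **The plan's own figures.** None is given for this outcome. The only sample-size figure, 200 women per group, is for loss to follow-up. It reproduces from the stated effect size of about 0.28 (5% taken as two-sided): 2 × ((1.960 + 0.8416)/0.28)² = 200.2. It does not bear on days to scheduling.

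**Inputs from the documents.** Control referral at about 30 days (Section 5; Table 1 says 3-4 weeks). A tracked window of 0-7 days for expert feedback under mIVAA (Section 12). Using that window for scheduling is an assumption, since feedback is not yet an appointment.

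**Inputs assumed.** Every share scheduled, and every delay other than those two. In the illustration, follow-up is taken as needed for all women in both arms.

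**Formulas.** For shares w scheduled at day d:

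- mean among scheduled = Σwd / Σw
- restricted mean over all women at horizon H = Σwd + (1 − Σw) × H

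**Case A: more women scheduled under mIVAA.** Control 60% at day 30; mIVAA 60% at day 7 and 30% at day 30.

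- Mean among scheduled: 30.0 vs (0.6×7 + 0.3×30)/0.9 = 13.2/0.9 = 14.7. Difference 15.3 days.
- Restricted mean, H = 90: 18 + 0.4×90 = 54.0 vs 13.2 + 0.1×90 = 22.2. Difference 31.8 days.
- The mean understates the gain. It also does so at H = 60 (42.0 vs 19.2) and H = 180 (90.0 vs 31.2).

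**Case B: fewer women scheduled under mIVAA.** Control 90% at day 30; mIVAA 50% at day 3.

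- Mean among scheduled: 30.0 vs 3.0, an apparent gain of 27 days.
- Restricted mean, H = 60: 27 + 6 = 33.0 vs 1.5 + 30 = 31.5, a gain of 1.5 days. At H = 90: 27 + 9 = 36.0 vs 1.5 + 45 = 46.5, a loss of 10.5 days.
- The mean flatters mIVAA, and how far depends on the horizon.

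**Case C: nearly all women scheduled.** Control 90% at day 30; mIVAA 90% at day 7 and 5% at day 60.

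- Mean among scheduled: 30.0 vs (6.3 + 3.0)/0.95 = 9.8. Difference 20.2 days.
- Restricted mean, H = 90: 36.0 vs 9.3 + 0.05×90 = 13.8. Difference 22.2 days.
- The two summaries nearly agree.

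**What fixed-day proportions would show (control vs mIVAA).**

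| Case | By day 7 | By day 30 |
|---|---|---|
| A | 0% vs 60% | 60% vs 90% |
| B | 0% vs 50% | 90% vs 50% |

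Both patterns are visible at once, without a rule for the missing dates.

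**When would the mean hide or reverse a real gain?** Let control average 30 days, a share *a* be scheduled at day 7 under mIVAA, and a further share *b* be scheduled at an average of L days. The mIVAA mean exceeds 30 when L > (30(a + b) − 7a)/b:

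- a = 0.5, b = 0.4: (27 − 3.5)/0.4 = 58.8 days
- a = 0.6, b = 0.3: (27 − 4.2)/0.3 = 76.0 days
- a = 0.8, b = 0.15: (28.5 − 5.6)/0.15 = 152.7 days

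The documented later route, Pap at about 30 days, falls well short of each. If the first group is instead scheduled only at day 25, the middle threshold drops to (27 − 15)/0.3 = 40.0 days, but day 25 lies far outside the 0-7 day feedback window.

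**The case against.** The strongest reply is that the problem may be close to empty. The Aim 2 methodology says VIA-positive women are referred under standard of care, and Section 4 puts the known 77% attrition after referral, among women who do not attend. If almost every referred woman gets a date, the mean is nearly sound (Case C). That stands as a limit on size. It does not settle the matter: Table 1 ties control referral to Pap results, the two statements need to be reconciled, and being referred is not the same as having a recorded scheduling date.

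It is also fair that the plan never states that the mean is restricted to scheduled women. That is the natural reading of an average in days; the fault is the missing denominator and rule. The plan does contain more than a mean: Section 12 lists the median and standard deviation among its descriptive statistics, and Section 5 intends to look at how quickly evaluation and appointment follow screening. Aim 2 says "Document timing of providing women who screen positive on VIA with colposcopist evaluation of cervical images and management plans", which commits the study to recording timing and is not a second instance of the defect. None of this is tied to a by-arm comparison that keeps women without a date.

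A reader might infer that the planned mean will hide or reverse a true gain from mIVAA. The documents do not support that. One can construct it: per 100 women, control has 40 scheduled at day 35; mIVAA has 60 at day 5 and 20 at day 120, giving (60×5 + 20×120)/80 = 33.75 against 35. But the 120 days has no source. With those 20 women at day 35 the mean is (60×5 + 20×35)/80 = 12.5 against 35, and the gain is plain. Even the constructed example does not reverse; that needs the late group to average over 125 days. Nor does the error run only against mIVAA, as Case B shows.

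**Conclusion.** The point holds in a limited form. The by-arm mean can be taken only over women with a scheduling date, the plan has no rule for the others, and it reports no percentage scheduled by arm. As the routes to scheduling differ, the mean can misstate the timing difference in either direction. With the documents' own timings, understating or overstating it is more plausible than a change of sign, which needs either very late extra scheduling under mIVAA or a large shortfall in the share scheduled. The documents show neither.

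The size cannot be given, because the share never scheduled is not documented; the cases above rest on assumed shares and delays. The outcome is secondary and descriptive, and the primary outcome is separate and unaffected. Minor severity, moderate confidence.

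**What to change.** In Section 12, replace the by-arm mean as the main timing summary with the following:

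1. Use the same denominator in both arms: VIA-positive women, counted from the screening date. The paragraph on record abstraction for historical controls should state this too, since it describes 200 screened women without giving VIA status.
2. Report the percentage ever scheduled, by arm.
3. Report the cumulative proportion scheduled by fixed days from screening, for example 7, 30, 60 and 90, with each woman's records searched to the last of these days in both arms.
4. Show women judged not to need follow-up as a separate category, treated as a competing outcome. They must not count as delayed; otherwise triage that correctly spares a visit would be scored as failure.
5. Take the median time from the cumulative-incidence curve, stated as not reached if under half are scheduled.
6. Keep the mean among scheduled women as descriptive, labelled as such and with its denominator.

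The cost is SAP wording and minor programming. The screening and scheduling dates are those the planned mean already needs. The Aim 2 list of historical data to abstract does not name the scheduling date, so it should be added there whichever summary is used.

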- Once health providers and staff are consented, screened and enrolled, we will work with La Liga to train midwives, nurse technicians who worked in mobile units, and colposcopists to use mIVAA (including use of the Pocket) and on research protocols including maintaining confidentiality of participant

data.

Midwives with assistance from nurse technicians

Activity 1: Use mIVAA system during VIA with consenting women

For each woman who consents to the use of mIVAA system, midwives will:

- Attempt to capture digital images of the cervix with mIVAA.
- Enter relevant clinical notes in mIVAA.
- Use mIVAA to send images of the cervix and of the VIA results form for each patient to participating expert colposcopist for evaluation of these images to evaluate the need for a management plan,
- For women with a positive VIA or suspicion of cancer, follow-up clinical evaluation with a colposcopist in a La Liga detection center will be scheduled based on feedback received from these same colposcopists as per La Liga's institutional protocols.
- For women without suspected lesions, further referrals may be made according to standard of care based on Pap results when available, and if positive.

Activity 2: Provide feedback on mIVAA through a brief survey and interviews, and/or an individual or group interview. Discussions will assess feedback and satisfaction with mIVAA. Individual or group interviews may be completed in person, by phone or by Zoom. The interviews will be audio recorded using an encrypted digital audio recorder, voice recording app on tablet or using Zoom's audio recording function.

Study staff will document in Spanish La Liga provider and staff feedback, and translate to English for analysis and inclusion in any publications. Interviews may be audio recorded, transcribed and translated.

Colposcopists

Activity 1: Use mIVAA system to access patient cervical screening documentation and communicate with midwives and staff at mobile unit.

For each patient, expert colposcopist will:

- Provide feedback on whether the patient should have a follow-up clinical evaluation.
- Rate quality of cervical image.

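### Midwife–colposcopist concordance is defined by two separate counts of positives, which cannot show whether the two readers flagged the same women

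*Combined protocol and SAP*

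**What the plan says.** In Section 12, under the secondary process outcomes, the plan lists "Concordance between midwife and colposcopist on women with suspected cancer or pre-cancer as measured by" two items: "Number of women screened positive by midwife" and "Number of women screened positive by expert colposcopist". Two other outcomes in the same list are also one-reader totals: "Percentage of mIVAA screened women with suspected cancer or pre-cancer by midwife" and "Percentage of mIVAA screened women with suspected cancer or pre-cancer by expert".

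No paired table, percent agreement or kappa for the cervical readings appears anywhere. The only inter-rater check in the plan concerns the coding of interview transcripts. The plan also does not say whether the concordance outcome belongs to Aim 1, Aim 2 or both.

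Who reaches the expert differs by aim (Section 5, midwives' Activity 1 under each aim):

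- **Aim 1** (about 102 women, not selected on VIA result): "For each woman who consents to the use of mIVAA system, midwives will" try to capture images and then "Use mIVAA to send images of the cervix and of the VIA results form for each patient" to the colposcopist.
- **Aim 2** (about 200 women): the midwife captures and sends images only when an enrolled woman is VIA-positive. VIA-negative women leave the study at that point.

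In both aims the colposcopist's listed output for each patient is a view on whether follow-up evaluation is needed, together with an image-quality rating. The system outcomes include "Percentage of mIVAA screened women with at least 1 image rated as readable by expert", so the plan allows for women whose images cannot be read.

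**The concern.** Concordance asks whether two readers classified the same women in the same way. Two totals answer a different question: whether the readers flagged similar numbers. Where the expert sees both midwife-positive and midwife-negative women, equal totals are compatible with complete agreement and with no shared positives at all. A report that follows the plan to the letter could present matching counts as good concordance when the readers had flagged different women.

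In Aim 2 the problem is different. Every imaged woman is VIA-positive, so if that is the midwife's positive result, expert positives are a subset of midwife positives. The counts then give a confirmation proportion, which the listed expert percentage already supplies in substance, while the listed midwife percentage is about 100% by design. Neither says anything about women the midwife called negative.

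The counts also have no denominator of women actually read. The gap between the two totals therefore mixes women the expert judged negative with women the expert could not judge.

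Remote expert review is one of the two components of mIVAA, so whether it changes who is flagged matters for interpreting the intervention.

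**Working it through.** The plan states no concordance figure, target or precision, so there is none to reproduce. The check is what two totals can and cannot determine.

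**Inputs.** N = 102 for Aim 1 and 200 for Aim 2 (Section 5). Midwife positives in Aim 1: m = 10, from the VIA positivity rate of about 10% given under Aim 2 (0.10 × 102 = 10.2). The expert count e is not documented, so it is assumed and varied.

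**Formulas.** Let a be the number of women positive by both readers. Given the margins,

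- max(0, m + e − N) ≤ a ≤ min(m, e)
- agreement = (N − m − e + 2a) / N
- chance agreement = [m·e + (N − m)(N − e)] / N²
- kappa = (agreement − chance) / (1 − chance)

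**Aim 1, N = 102, m = 10**

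| Assumed e | Possible a | Agreement | Kappa |
|---|---|---|---|
| 5 | 0 to 5 | 85.3% to 95.1% | -0.07 to 0.64 |
| 10 | 0 to 10 | 80.4% to 100% | -0.11 to 1.00 |
| 15 | 0 to 10 | 75.5% to 95.1% | -0.13 to 0.77 |
| 20 | 0 to 10 | 70.6% to 90.2% | -0.15 to 0.62 |

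Worked case, e = 10: with a = 0, agreement is (102 − 20)/102 = 82/102 = 80.4%. With a = 10, it is 102/102 = 100%. Chance agreement is (100 + 92 × 92)/10,404 = 0.823, so kappa at the lower bound is (0.804 − 0.823)/0.177 = -0.11. The plan's reported result, 10 and 10, is identical in both cases. Only totals of 0 or N would fix the overlap.

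**Both aims combined** (the plan neither proposes nor excludes this): N = 302 and m = 10 + 200 = 210. With an assumed e = 210, a runs from 118 to 210 and agreement from 118/302 = 39.1% to 100%.

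**Aim 2, N = 200, all midwife-positive.** Here a = e, so agreement reduces to e/200, and kappa is 0 (undefined if e = 200). The remaining issue is the denominator. With an assumed 150 expert positives (Wilson 95% CI):

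| Women without an expert reading (assumed) | Confirmation share | 95% CI |
|---|---|---|
| 0 | 150/200 = 75.0% | 68.6% to 80.5% |
| 20 | 150/180 = 83.3% | 77.2% to 88.1% |
| 40 | 150/160 = 93.8% | 88.9% to 96.6% |

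The two counts, 200 and 150, are the same in all three rows.

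**The case against.** The strongest reply is that the outcome list is meant for Aim 2. The table is introduced as evaluation outcomes, evaluation is the term used for Aim 2, several items are split by study arm, and concordance is not among the Aim 1 pilot objectives. On that reading the counts do yield the confirmation share, the label is mostly a matter of wording, and no table could recover agreement on negatives that the design never collects. This is plausible, but it is an inference. The plan does not assign the outcome to an aim, and a midwife percentage that is about 100% by design in Aim 2 argues against it. Even if it is right, the denominator of women read is still missing.

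Four further points deserve weight:

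- **The lower bounds are mathematical extremes.** The expert receives the midwife's VIA result with the images, so zero overlap is unlikely in practice. That is fair, but the totals still leave the value open.
- **Positivity is partly defined.** Section 5 describes VIA-positive as any whitening, and Table 1 links a positive expert review to referral. What remains open is how either maps to suspected cancer or pre-cancer.
- **Unreadable images and time to expert feedback are reported separately.** They are, but those items do not give the number of women with both readings.
- **Nothing is irrecoverable.** Results are held per woman, and this is one descriptive secondary outcome. That limits the seriousness, but it does not make the stated measure valid.

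**Conclusion.** The concern holds. As written, the concordance outcome cannot show agreement. In Aim 1, or if the aims were combined, the two counts leave it undetermined: from 80.4% to 100% for 10 and 10 positives among 102 women, with similarly wide kappa ranges at the other expert counts tried. In Aim 2 they give at most an expert confirmation proportion, and that only if every imaged woman is read and VIA-positive is the midwife's positive result. Section 5 supports the latter, but the plan does not define it. If suspected cancer or pre-cancer is narrower than VIA-positive, the Aim 2 overlap is not fixed by the counts either.

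The expert counts and numbers unread are assumptions for illustration. That two totals do not determine agreement does not depend on them. The primary comparison of loss to follow-up is unaffected, so this is worth correcting but does not threaten the main result.

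**What to change.** Replace the two counts in Section 12 with a per-woman midwife-by-expert cross-tabulation among women with both readings, shown separately by aim, and report how many women have no expert reading.

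- **Aim 1:** report overall agreement, and agreement among midwife positives and among midwife negatives, each with a 95% CI. Kappa is optional.
- **Aim 2:** report the proportion of VIA-positive women with an expert reading whom the expert confirms, with a 95% CI. Do not call it concordance or pool it with Aim 1.
- **Definitions:** state which recorded midwife result (VIA-positive or suspicion of cancer) and which expert result count as positive.
- **Interpretation:** state that the expert sees the VIA result, so the readings are not independent.

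The cost is mainly SAP wording. The VIA result and the expert's feedback are produced for each woman, and Section 14 says mIVAA holds study IDs with clinical information. If no field records expert-suspected cancer or pre-cancer, either the follow-up feedback must be defined as the expert result or a field must be added. The drawback is precision: agreement on positives in Aim 1 rests on about 10 women, and 8 of 10, for example, has a 95% CI of 49% to 94%.
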